#### 2. Bile duct matching model

In addition to the criteria mentioned in the bile duct segmentation model, the bile duct matching model should also meet the following criteria:

- 1) Able to complete MRCP in prone position;
- 2) Bile ducts are almost completely visible in MRCP and ERCP.

#### 3. Clinical trials

In addition to the criteria mentioned in the bile duct segmentation model, the clinical trials should also meet the following criteria:

- 1) Able to complete MRCP in prone position;
- 2) Patients requiring biliary drainage by ERCP due to malignant hilar biliary obstruction.

### 3.2. Exclusion criteria

All patients meeting the following criteria will not be considered for participation in the study:

#### 1. Bile duct segmentation model and bile duct matching model

- 1) Has participated in other clinical trials, signed the informed consent and was in the follow-up period of other clinical trials;
- 2) Drug or alcohol abuse or psychological disorder in the last 5 years;
- 3) Patients in pregnancy or lactation;
- 4) The investigator considers that the subjects were not suitable for MRCP, ERCP and related tests;
- 5) A high-risk diseases or other special conditions that the investigator considers inappropriate for the subject to participate in a clinical trial.

#### 2. Clinical trials

In addition to the criteria mentioned in the above, the clinical trial must not meet any of the following criteria:

- 1) Previous gastrectomy;
- 2) Stent replacement;
- 3) Pyloric or duodenal obstruction.

### **3.3. Definition of enrollment**

After participants signed informed consent, they were randomized before ERCP. The randomization time was the enrollment time, and was recorded in CRF.

## **4. Endpoints**

### **4.1. Primary Endpoint**

- 1) Procedure time: It was the time of performing ERCP.

### **4.2. Secondary Endpoints**

- 1) Intersection over union of bile duct segmentation: It was the ratio of union and intersection of bile ducts predicted by artificial intelligence devices and actual bile ducts
- 2) Intersection over union of bile duct matching model: It was the ratio of union and intersection between the bile ducts generated by the AI device and the actual bile ducts in ERCP
- 3) Success rate of stent placement: It was calculated by dividing total number of patients with stent placement by the number of successful patients.
- 4) Rate of adverse events: It was calculated by dividing the total number of patients undergoing stent placement by the number of patients who experienced adverse events.
- 5) Fluoroscopy time: It was the sum of the total X ray fluoroscopy time during the whole procedure.
- 6) Total amount of contrast medium: It was the total amount of contrast medium during the whole procedure.

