### **8.2. Methods**

Continuous variables should be described by number of subjects, mean, standard deviation, median, minimum and maximum. The classification variables are summarized by frequency and percentage.

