### **8.3. Hypothetical test**

The main assumptions are:

1. The use of EndoAngel can reduce the operation time of ERCP;
2. The use of EndoAngel can improve the success rate of stent placement;
3. The use of EndoAngel can reduce the rate of adverse events;
4. The use of EndoAngel can reduce the fluoroscopy time;
5. The use of EndoAngel can reduce the total amount of contrast medium.

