## 8.4. Sample Size Calculation

We mainly studied the effect of EndoAngel on the quality of ERCP for physicians. Therefore, data collection and analysis were conducted for the main effect. It is expected that a total of 62 subjects will be enrolled. Assuming the operation time of ERCP in experimental group is  $43.9 \pm 11.56$  minutes, the operation time of ERCP in control group is 35 minutes. Bilateral significance level 5% ( $\alpha = 5\%$ ), assurance 80% ( $\beta = 20\%$ ), shedding rate 10%, Expected to enroll 62 patients in total.

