## 8.5. Statistical analysis set

All patients who met the inclusion and exclusion criteria were considered eligible for recruitment.

The two analysis sets in this study are defined as follows:

- The full analysis set (FAS) population analysis set will contain all eligible cases and shedding cases, but does not include culling cases.
- The Compliance (PP) population analysis set will include all subjects in the FAS analysis set with no significant deviation from the program.

Intention-to-treat and conformity analysis sets should be used to analyze the primary efficacy endpoints. The main analysis will be based on the PP analysis set. FAS analysis was regarded as supportive analysis.

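### Section 4.2 exchanges numerator and denominator in the stent-success rate and the adverse-event rate

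*Protocol*

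**What the plan says.** Section 4.2 of the protocol lists six secondary endpoints and gives formulas for two rates.

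- Item 3, the stent-success rate: "It was calculated by dividing total number of patients with stent placement by the number of successful patients".
- Item 4, the adverse-event rate: "It was calculated by dividing the total number of patients undergoing stent placement by the number of patients who experienced adverse events".

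The summary (section 1) and section 7.1 name both endpoints without a formula, and section 4.3 covers only the recording and grading of adverse events. No other section restates or corrects the two definitions.

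Two later sections bear on what was meant. Section 8.2 says: "The classification variables are summarized by frequency and percentage". Section 8.3 gives the expected directions: hypothesis 2 is "The use of EndoAngel can improve the success rate of stent placement" and hypothesis 3 is "The use of EndoAngel can reduce the rate of adverse events".

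Items 1 and 2 of section 4.2, the intersection-over-union measures, have correct titles, but their explanations name the union first. Item 1 reads: "It was the ratio of union and intersection of bile ducts predicted by artificial intelligence devices and actual bile ducts".

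**The concern.** To divide A by B is to form A/B. Both items therefore define a patient total over the count of interest, which is the reciprocal of a proportion. Such a quantity cannot be summarised as an ordinary percentage, and it moves the wrong way: more successes lower the success figure, and more patients with adverse events lower the adverse-event figure. Read literally, hypotheses 2 and 3 would be met by fewer successes and by more patients with adverse events.

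Two of the five hypotheses in section 8.3, one of them the safety hypothesis, rest on these definitions. Whoever programs or reports them must set the written formula aside and supply another.

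**Working it through.** The protocol gives no expected success or adverse-event rate, so there is no figure of its own to reproduce. The check is to evaluate each formula as written and with its terms exchanged.

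**Inputs**
- N = 31 per arm: 62 patients (section 8.4) at 1:1 allocation (section 6.5.1), 62/2 = 31.
- x = number of successful patients, or of patients with an adverse event, in an arm. All values of x below are assumptions for illustration.

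**Formulas**
- As written: N/x.
- With the terms exchanged: x/N.

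**Range.** Successful patients are a subset of the patients with stent placement, so x ≤ N and N/x ≥ 1. The written success rate is therefore at least 100% and equals 100% only when every placement succeeds. For adverse events, x = 0 gives 31/0, which is undefined; the exchanged formula gives 0/31 = 0%.

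**Single-arm values**

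| Endpoint | x of 31 | As written | Exchanged |
|---|---|---|---|
| Success | 25 | 31/25 = 124.0% | 25/31 = 80.6% |
| Success | 28 | 31/28 = 110.7% | 28/31 = 90.3% |
| Success | 30 | 31/30 = 103.3% | 30/31 = 96.8% |
| Adverse events | 1 | 31/1 = 3100% | 1/31 = 3.2% |
| Adverse events | 3 | 31/3 = 1033% | 3/31 = 9.7% |
| Adverse events | 5 | 31/5 = 620% | 5/31 = 16.1% |

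**Direction between arms**, with EndoAngel assumed to be the better arm

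| Endpoint | Counts, EndoAngel vs control | As written | Exchanged |
|---|---|---|---|
| Success | 30 vs 27 | 103.3% vs 114.8% | 96.8% vs 87.1% |
| Adverse events | 2 vs 4 | 1550% vs 775% | 6.5% vs 12.9% |

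On both endpoints the written formula gives the better arm the worse figure.

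**What does not change.** A test on the two-by-two table uses the counts x and N - x in each arm and never uses the ratio, so its result is the same. Section 8.4 sizes the trial on operation time alone, so the primary endpoint and N = 62 are untouched.

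**The case against.** The strongest reply is that nobody would be misled. The endpoints are called rates, section 8.2 asks for percentages and section 8.3 fixes the direction; only the usual proportion fits all three. The slip is probably one of wording or translation, and figures such as 1033% would appear only if someone applied a formula that plainly cannot give a sensible percentage. All of this stands, and it limits the weight of the point. It does not make the text correct: this is the operative definition of two endpoints, and nothing elsewhere in the protocol replaces it.

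A reader might infer three stronger things, which the protocol does not support.

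- **That the two rates count different populations.** Item 4 does not expressly limit the patients with adverse events to those undergoing stent placement, so one could suspect that a patient whose ERCP was aborted counts as an event but not in the total. The natural reading is that they are among the patients just named. The total may also mean the whole treated population, since section 3.1 admits only patients who need drainage. Section 6.4 keeps data collected before discontinuation, and section 8.5 states: "The full analysis set (FAS) population analysis set will contain all eligible cases and shedding cases, but does not include culling cases". Which analysis set each secondary rate uses, and how aborted procedures count, are commonly settled in a statistical analysis plan, which is not at hand. Nor can the effect be sized from section 8.4 ("shedding rate 10%, Expected to enroll 62 patients in total"), because that is a general dropout allowance and not a rate of aborted procedures.
- **That an undefined adverse-event rate is likely.** The chance of an arm without any affected patient depends on an adverse-event risk that the protocol does not give.
- **That intersection over union is also defined upside down.** A ratio of two named quantities does not say which is divided by which, and the titles of items 1 and 2 do. This is loose wording only.

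**Conclusion.** The point holds for items 3 and 4 of section 4.2: numerator and denominator are exchanged in both. The success rate as written cannot be below 100%, the adverse-event rate has no value when no patient is affected, and both run opposite to hypotheses 2 and 3. These conclusions follow from the wording alone; only the illustrative percentages depend on assumed counts.

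The weight is modest. It is a certain error in the definition of two secondary endpoints, with an intent that can be inferred, and with no effect on tests of the counts, on the primary endpoint or on the sample size. It should be fixed because the definition is wrong as it stands and the correction is trivial.

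**What to change.** Reword section 4.2 as follows.

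- Item 3: success rate = number of patients with successful stent placement / number of patients with stent placement.
- Item 4: adverse-event rate = number of patients, among those undergoing stent placement, who had at least one adverse event / number of patients undergoing stent placement.
- Items 1 and 2, in the same edit: area of intersection divided by area of union, to match the titles.

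The cost is a few words in one section. Design, sample size, data collection and the hypotheses in section 8.3 stay as they are.

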### 1.2. Flow chat

## 2. Introduction

Biliary stricture can be divided into benign biliary stricture and malignant biliary stricture, and malignant hilar biliary obstruction is the one of the common cause. Since there is no specific early screening method for malignant hilar biliary obstruction at present and most patients have no obvious clinical symptoms in the early stage, most patients are already in the advanced stage when they are first diagnosed. Advanced malignant hilar biliary obstruction cannot undergo resection surgery, whose first choice for the treatment is palliative endoscopic biliary drainage. Biliary drainage can relieve jaundice, pruritus and other symptoms due to cholestasis. However, before the narrow segment was placed the stent, the contrast agent could not pass through the narrow segment and the bile duct above the narrow segment could not be seen. So it was difficult for doctors to determine the direction of the guide wire and the position of the stent. In addition, indiscriminate application of the contrast agent may cause outflow obstruction leading to infection. However, there is no relevant research to solve these problems.

MRCP is the preferred examination method of pancreatic and bile duct diseases. Therefore, MRCP should be routinely performed before patients are treated with ERCP. At present, MRCP is in supine position, and ERCP is in prone position. Different positions lead to differences in the morphology of MRCP and the bile duct on ERCP. So preoperative MRCP in supine position has limited role in advising physicians on the morphology of the bile duct. Therefore, MRCP in the prone position is more favorable for endoscopists to perform ERCP.

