#### **6.4.2 Intraprocedure**

For safety reasons, the investigator may have the subject quit during the procedure. For example, the patient is not suitable for receiving the instrument for the study or the endoscopists do not use the specified instrument for any reason. If the following serious cases occur, please withdraw during the operation:

- 1) Perforation
- 2) Bleeding
- 3) Allergy to narcotic drugs
- 4) Unable to complete ERCP due to obstruction or other reasons

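### Section 4.2 ties the adverse-event and stent-success rates to patients who reach stent placement, so some randomised patients may fall outside both rates

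*Protocol*

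**What the plan says.** Section 4.2 defines the two rates in words. Stent success is obtained by "dividing total number of patients with stent placement by the number of successful patients", and the adverse-event rate by "dividing the total number of patients undergoing stent placement by the number of patients who experienced adverse events". Both divisions are written upside down. That is a separate error; here I take the evident intent, with the stent-placement group as the denominator: "the total number of patients undergoing stent placement" for adverse events and "total number of patients with stent placement" for success.

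Four other parts of the protocol bear on that group:

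- **Time of randomisation.** Section 3.3 states: "After participants signed informed consent, they were randomized before ERCP". Section 6.5.1 agrees.
- **Stopping during the procedure.** Section 6.4.2 instructs: "If the following serious cases occur, please withdraw during the operation". It then lists perforation, bleeding, allergy to narcotic drugs, and "Unable to complete ERCP due to obstruction or other reasons". Under 6.4.3 these patients are not replaced.
- **Data kept.** Section 6.1 has adverse events during the procedure entered on the CRF for later analysis. Section 6.4 retains data collected before a discontinuation.
- **Use of the rates.** Hypotheses 2 and 3 in section 8.3 are that EndoAngel raises stent success and lowers the adverse-event rate.

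Sections 4.3, 7.1 and 8.5 give no other denominator for either rate. Section 8.5 defines FAS and PP sets but assigns them only to the primary efficacy endpoints.

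**The concern.** Whether a patient reaches stent placement is settled after randomisation, in a procedure that the device is designed to steer: the Summary and section 5.1 say that EndoAngel guides the wire and the position of the stent. A denominator that depends on reaching this step depends on something the assigned arm may change. The groups compared are then not the groups that were randomised.

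Section 6.4.2 foresees procedures that cannot be completed, and three of its four reasons for withdrawal are themselves adverse events. A patient stopped for such an event before stenting has a recorded event but no stated place in the rate. At stake are two of the five hypotheses in 8.3, one of them on the only safety rate that 4.2 defines. Turning the two fractions the right way up would leave this problem in place.

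**Working it through.** **1. The plan's own figure.** The only relevant stated number is the sample size of 62 (section 8.4), from means of 43.9 and 35 minutes (difference 8.9), SD 11.56, two-sided 5% and 80% power. By the normal approximation, n per arm = 2 × (1.960 + 0.842)² × 11.56² / 8.9² = 26.5, so 27 per arm and 54 in total; 54/0.9 = 60. A t-test calculation gives 28 per arm and 56 in total; 56 × 1.1 = 61.6, rounded up to 62. The figure is reproduced. It rests on procedure time alone, so the present point leaves it unchanged. With 1:1 allocation (6.5.1) there are 62/2 = 31 patients per arm.

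**2. Who is outside the denominator.** The wording allows two readings.

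- *A stent was placed.* Every patient without a stent is outside both rates, whether the wire did not cross or the procedure was stopped. If success means that a stent is in place, the success rate tends towards 100%.
- *Stenting was attempted.* Failed attempts are inside. Patients stopped before any attempt are still outside.

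On neither reading does the denominator cover all randomised patients in whom ERCP was started.

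**3. Size on the first reading, with assumed counts.** The protocol gives no stent-failure or adverse-event rate. Assume 31 patients with ERCP started in one arm, f of them without a stent and all f with an event, and 3 stented patients with an event. Take success as a stent in place.

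| f | Events in stented / stented | All events / stented | All events / ERCP started | Success / stented | Success / ERCP started |
|---|---|---|---|---|---|
| 0 | 3/31 = 9.7% | 3/31 = 9.7% | 3/31 = 9.7% | 31/31 = 100% | 31/31 = 100% |
| 1 | 3/30 = 10.0% | 4/30 = 13.3% | 4/31 = 12.9% | 30/30 = 100% | 30/31 = 96.8% |
| 3 | 3/28 = 10.7% | 6/28 = 21.4% | 6/31 = 19.4% | 28/28 = 100% | 28/31 = 90.3% |
| 6 | 3/25 = 12.0% | 9/25 = 36.0% | 9/31 = 29.0% | 25/25 = 100% | 25/31 = 80.6% |

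For f = 1, 3 and 6 the stented-only event rate is about 3, 9 and 17 points below the rate over all started procedures. If every event is counted but only stented patients form the denominator, the rate is too high instead.

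**4. Direction.** If the unstented patients have no event, the stented-only rate is slightly too high: for f = 3, 3/28 = 10.7% against 3/31 = 9.7%. The sign therefore depends on counts that the protocol does not give.

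**5. Between arms.** Suppose one arm has f = 1 and the other f = 3, as in the table. Over all started procedures the event rates are 12.9% and 19.4%, a difference of 2/31 = 6.5 points. Over stented patients they are 10.0% and 10.7%, a difference of 0.7 points.

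**6. Size on the second reading.** Take f = 3 and assume that one of the three was stopped before any attempt. The denominator is 30. The event rate is 5/30 = 16.7% against 6/31 = 19.4%, and success is 28/30 = 93.3% against 28/31 = 90.3%. The gap is smaller but remains.

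**The case against.** The strongest reply is that *undergoing* naturally describes having the procedure, whatever its result. Section 4.2 also separates patients with stent placement from successful patients, which makes sense only if some in the first group can fail. In addition, section 3.1 admits to the trial only patients who need biliary drainage by ERCP for malignant hilar obstruction. On that reading nearly all randomised patients are in the denominator, including one whose wire does not cross. This largely stands. A reader might infer that the plan excludes all failed placements and makes success 100% by construction; the text supports this on one reading only. But the attempted reading still leaves out patients stopped before an attempt, and the use of *with* in one sentence and *undergoing* in the next leaves the reading open.

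A reader might also infer that the harm of failed procedures is lost. It is not: 6.1 and 6.4 keep the records, and the schedule in 1.1 collects adverse events without regard to stenting. What is missing is a denominator that matches them.

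Nor does the Introduction single out the unstented patient. Its remark that "indiscriminate application of the contrast agent may cause outflow obstruction leading to infection" concerns the use of contrast, not failed stenting. Likewise, perforation and bleeding in 6.4.2 can occur before or after a stent is placed, so they do not by themselves identify unstented patients.

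Finally, a statistical analysis plan might exist and refine the rates. But the protocol has already fixed the definitions, and a plan that follows them would inherit the problem.

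**Conclusion.** The point holds. On either reading of 4.2, some randomised patients in whom ERCP is started can fall outside both rates, and no other section gives a wider denominator. Hypotheses 2 and 3 in 8.3 would then be examined in groups formed after randomisation.

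The size and direction cannot be stated from the protocol. A reader might infer a bias in favour of EndoAngel, but nothing in the document supports a particular sign. The percentages above rest wholly on assumed counts and show only that, with 31 per arm, one patient moves a rate by about 1/31 = 3.2 points. If every patient is stented, all versions agree. The primary endpoint and the sample size are unaffected. Since both rates are secondary endpoints, this should be fixed but does not threaten the main analysis.

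**What to change.** Replace the two definitions in section 4.2:

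- Adverse-event rate = randomised patients in whom ERCP was started and who had at least one adverse event, divided by all randomised patients in whom ERCP was started.
- Stent success = patients with successful stent placement, divided by the same denominator, with patients without a successful stent counted as failures.

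State that both are analysed by assigned arm. The same edit can put the inverted fractions right.

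The cost is two sentences, with no change to the sample size and no new data item. Because 6.4 speaks only of data before discontinuation, it would help to confirm that patients withdrawn during ERCP keep the adverse-event follow-up scheduled in 1.1. The one drawback is that the reported success rate may look slightly lower.

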### **4.3. Safety evaluation endpoints and other secondary endpoints**

Adverse events shall be determined according to the definition in the code for the quality management of adverse events of medical devices. The following types of adverse events should be recorded and calculated in the hospital history and CRF. According to the CRF table, the

occurrence time, starting and ending time, intervention measures and treatment results should be filled in when recording. The severity should be referred to the previous literature and CTCAE 5.0 standard.

## **5. Purpose and overall design**

### **5.1. Purpose**

The purpose of this study is to develop an artificial intelligence-based biliary stricture navigation system in MRCP-based ERCP, which can instruct the direction of guide wire and the position of stent placement in real time.

### **5.2. Overall design**

This is a prospective, single-center, randomized controlled trial study.

